## 15.2 Pharmacokinetic Summaries

### 15.2.1 Pharmacokinetic Concentrations

Plasma concentrations for BMS-986251 below the limit of quantification (BLQ) will be set to zero in the computation of mean concentration values. Descriptive statistics (n, mean, SD, geometric mean, %CV, median, min, and max) will be used to summarize the plasma concentrations by treatment at each scheduled time point. If over 50% of the subjects in a given cell have values BLQ, then the descriptive statistics will not be presented and will instead display as BLQ for the mean and minimum. With the exceptions of n and maximum, all other statistics will be missing.

Linear and semi-logarithmic plots of the arithmetic mean plasma concentrations + SD by scheduled sampling times will be provided for Part A, the treatments will be presented in one plot. These plots will show time in hours. The plots will match the summary table results and will not have an observation at a given time point if more than half of the subjects have values BLQ. Linear plots will be presented to 24 hours and to the last scheduled time point. Semi-log plots will be presented to the last scheduled time point. The linear and semi-logarithmic plots will be presented side-by-side on a single page.

Linear and semi-logarithmic plots of the individual plasma concentrations by actual sampling times will be provided by subject. These plots will show time in hours. Individual plots will use the BLQ handling procedure described below for "Pharmacokinetic Parameters". Linear plots will be presented to 24 hours and semi-log plots will be presented to the last scheduled time point.

Linear and semi-logarithmic spaghetti plots of the individual plasma concentrations by actual sampling times will be provided by treatment. These plots will show time in hours. Spaghetti plots will use the BLQ handling procedure described below for "Pharmacokinetic Parameters". Linear plots will be presented to 24 hours and semi-log plots will be presented to the last scheduled time point.

All individual subject plasma concentration data will be listed, including time deviations and comments.

### 15.2.2 Pharmacokinetic Parameters

PK parameters for BMS-986251 will be estimated using non-compartmental methods with WinNonlin®. The plasma PK parameters will be estimated from the concentration-time profiles. In estimating the PK parameters, BLQ values at the beginning of the profile will be set to zero. BLQ values that occur after the first quantifiable point will be considered missing. Values that are embedded between BLQs, or quantifiable values occurring after two or more BLQs, will be set to missing at the discretion of the pharmacokineticist. Actual sampling times, rather than scheduled sampling times, will be used in all computations involving sampling times. If the actual time or dose time is missing, the scheduled time may be substituted in order to calculate the PK parameter.

Descriptive statistics (n, mean, SD, geometric mean, %CV, median, min, and max) will be used to summarize the calculated PK parameters by treatment. For Tmax, only n, median, min and max will be presented.

The points to be included in the Lz range will be from the WinNonlin best fit generated profiles. At least 3 points will be required to be used. The Cmax data point will not be included.

### 15.2.3 Statistical Analyses

#### 15.2.3.1 Dose-proportionality

The pharmacokinetic parameters Cmax, AUC(0-T), and AUC(INF) for BMS-986251 from the Part A groups will be compared across each dose level to assess dose proportionality. Dose proportionality will be assessed by estimating the slope of the linear regressions of natural logarithmic transformed AUC(0-T), AUC(INF), and Cmax on log(dose).

Statistical analyses will be done using a power model (Gough et al, 1995) with mixed effects of the following general form,

$$\ln(\text{PK}) = \ln(\beta_0) + \beta_1 \cdot \ln(\text{Dose}) + \epsilon,$$

where

PK is the pharmacokinetic parameter tested (e.g., Cmax or AUC)

$\ln(\beta_0)$  is the y-intercept,

$\beta_1$  is the slope (a value of  $\beta_1 = 1$  indicates linearity), and

$\epsilon$  is an error term

The estimate of  $\beta_1$  and 90% CI will be reported along with the associated p-value and the dose range for proportionality. A significant difference from unity (1) and lack of proportionality will be defined as  $p < 0.05$ .

Plots of AUC(0-T), AUC(INF) and Cmax versus dose on the linear scale and the equation line will be provided to assess dose proportionality.

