**Table 4 Plasma BMS-986251 PK Parameters- Part A (SAD Part)**

Parameter	SAD Part	MAD Part Day 1*	Description	SAS Programming Notes
Cmax	X	X	Maximum plasma concentration. Observed peak analyte concentration obtained directly from the experimental data without interpolation, expressed in concentration units	Cmax from WNL
Tmax	X	X	Time to maximum plasma concentration. First observed time to reach peak analyte concentration obtained directly from the experimental data without interpolation, expressed in time units.	Tmax from WNL
AUC(0-T)	X	X	Area under the concentration-time curve (time 0 to time of last quantifiable concentration).	AUClast from WNL
AUC(INF)	X	X	Area under the plasma concentration-time curve (time 0 to infinity). A valid half-life is required to retain this parameter.	AUCINF_obs from WNL If T-HALF is present.
AUC%Extrap	X	X	Percentage of the AUC(INF) that is extrapolated.	AUC_%Extrap_obs from WNL– Listed only
T-HALF	X	X	Terminal phase half-life expressed in time units. A valid Lz is required to retain.	HL_Lambda_z from WNL
Lz	X	X	Terminal phase rate constant calculated by the WinNonlin generated best fit linear regression of the terminal log-linear portion of the concentration vs. time curve. Linear regression of at least 3 points and an adjusted R2 > 0.80 are required to retain.	Lambda_z from WNL.
CL/F	X	X	Apparent clearance	CL_F_obs from WNL
Vd/F	X	X	Apparent volume of distribution at terminal phase	Vz_F_obs from WNL
Adj R 	X	X	Adjusted R  value of terminal elimination phase	Rsquared adjusted from WNL – Listed only

Parameter	SAD Part	MAD Part Day 1*	Description	SAS Programming Notes
Lz_Start	X	X	The time point starting the log-linear elimination phase defining their terminal half-life	Lambda_z_lower from WNL – Listed only
Lz_End	X	X	The time point ending the log-linear elimination phase defining the terminal half-life	Lambda_z_upper from WNL – Listed only
Lz_N	X	X	Number of time points in the log-linear elimination phase defining the terminal half-life	No_points_lambda_z from WNL – Listed only

Note: AUCs will be calculated using linear up / log down, expressed in units of concentration x time.

\* There are only 2 subjects in cohort B1 who have been dosed till Day 10. PK parameters will be calculated for Part B (MAD part) Day 1 if feasible.

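### The p<0.05 proportionality rule is applied to AUC(0-T), whose slope is biased above 1 for a proportional drug if 2 mg profiles fall below the assay limit before about 144–192 h

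*SAP*

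**What the plan says.** SAP 15.2.3.1 states that, together with Cmax, "AUC(0-T), and AUC(INF) for BMS-986251 from the Part A groups will be compared across each dose level to assess dose proportionality". It does this by "estimating the slope of the linear regressions of natural logarithmic transformed AUC(0-T), AUC(INF), and C max on log(dose", using a power model. It then sets a decision rule: "lack of proportionality will be defined as $p < 0.05" (closing symbol lost in the text conversion). It also states that the slope's "90% CI will be reported along with the associated p-value and the dose range for proportionality".

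The end of AUC(0-T) is set elsewhere. SAP Table 4 defines it as "Area under the concentration-time curve (time 0 to time of last quantifiable concentration", and SAP 15.2.2 adds that "BLQ values that occur after the first quantifiable point will be considered missing". The integration end time is therefore specific to each subject.

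For AUC(INF), Table 4 says "A valid half-life is required to retain this parameter". A valid half-life needs at least 3 points and an adjusted R² above 0.80, and the Cmax point is excluded (SAP 15.2.2). AUC%Extrap is calculated but only listed. No common-window AUC is planned for Part A, and nothing says which AUC governs if the two disagree. SAP 8.4.3 states that no formal hypothesis testing will be done.

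**The concern.** The power model reads a slope above 1 as exposure rising faster than dose. That reading needs the same quantity to be measured at every dose. The Part A doses run from 2 to 60 mg, a 30-fold range. At a half-life of about 40 h (protocol 8.1.1), a 60 mg profile reaches any fixed assay limit log2(30) = 4.9 half-lives, about 196 h, later than a proportional 2 mg profile. If the 2 mg samples become unquantifiable within the 240 h schedule, AUC(0-T) leaves out more of the tail at 2 mg than at 60 mg. The log-log slope then rises although clearance is constant.

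At stake is a clinical study report that labels a proportional drug non-proportional on one of its two AUC measures, or gives two conflicting AUC results with no rule for choosing between them. The confidence interval for the AUC(0-T) slope would be shifted in the same way.

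**Working it through.** **Inputs from the documents.** Doses 2, 6, 15, 30 and 60 mg (SAP 8.2.2). Six active subjects in each of A1–A4 (SAP Table 1). Four subjects dosed in A5 (SAP 7.1), active number not stated. Anticipated half-life about 40 h (protocol 8.1.1). Sampling at 48, 72, 96, 120, 144, 192 and 240 h among other times (SAP Table 8). Rule p<0.05.

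**Assumptions.** True slope exactly 1; one-compartment decline; 3 active in A5 (27 in total); CV 30%, range 20–40%; two-sided test; one value per subject, so ordinary regression. The assay limit (LLOQ) is not in the public text, so results are indexed by the last quantifiable time at 2 mg.

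**Plan's own figure.** The only stated error rate is the nominal 5%. With no truncation, the calculation below returns 5.0%, and simulated trials gave 4.4–4.6%.

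**Step 1: end times.** T(d) = T(2 mg) + 40·log2(d/2). The added times are 63, 116, 156 and 196 h at 6, 15, 30 and 60 mg. Each T is moved back to the preceding scheduled sample, with a maximum of 240 h.

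**Step 2: share captured.** F = 1 − 2^(−T/40). For T(2 mg) = 48 h the end times are 48, 96, 144, 192 and 240 h, so F = 0.565, 0.811, 0.918, 0.964 and 0.984.

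**Step 3: slope bias.** Bias = Σ(x − x̄)·ln F / Sxx, with x = ln(dose), x̄ = 2.365 and Sxx = 34.86. At 48 h: 5.96/34.86 = 0.171.

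**Step 4: rejection.** σ = √ln(1 + 0.30²) = 0.294 and SE = 0.294/√34.86 = 0.050. The noncentrality is 0.171/0.0497 = 3.44 on 25 df with critical value 2.060, giving 91%.

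| 2 mg last quantifiable | Implied LLOQ, % of 2 mg peak | Mean slope | False rejection, CV 30% | CV 20% to 40% |
|---|---|---|---|---|
| 48 h | 44% | 1.17 | 91% | 100% to 71% |
| 72 h | 29% | 1.10 | 46% | 79% to 30% |
| 96 h | 19% | 1.06 | 22% | 42% to 15% |
| 120 h | 12.5% | 1.04 | 12% | 21% to 9% |
| 144 h | 8% | 1.02 | 7% | 10% to 6% |
| 192 h | 4% | 1.01 | 5% | 5% to 5% |
| 240 h | 1.6% | 1.00 | 5% | 5% to 5% |

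The second column is 2^(−T/40). In this model it is also the share of AUC(INF) that must be extrapolated at 2 mg. With 2 to 4 active subjects in A5, the CV 30% results are 90–92% at 48 h and 45–48% at 72 h, and move by less than 1 point elsewhere.

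**Step 5: check by simulation.** This used scheduled times, the SAP's linear-up/log-down rule, ka 1/h, 10% residual error and 4,000 trials per setting. At CV 30%, one-compartment, AUC(0-T) was rejected in 5.4% of trials with LLOQ at 1/32 of the 2 mg Cmax, 6.2% at 1/20, 11% at 1/10, 32% at 1/5 and 72% at 1/3. With a marked distribution phase (70% of the intercept at a 6 h half-life, 30% at 40 h) it was 5.4% at 1/64, 12% at 1/20, 34% at 1/10 and 85% at 1/5.

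**Step 6: alternatives.** AUC(INF), checked one-compartment only with 500–600 trials per setting, was rejected in 3.8–5.8% of trials for LLOQ up to 1/5 of the 2 mg Cmax and 5.6–7.6% at 1/3. Cmax stayed at about 4–5%. AUC(0-24) gave a mean slope of 1.00 and 4.8–5.7% in every setting. It needs 2 mg samples quantifiable at 24 h. That held for at least 91% of subjects, except about 40% in the two-compartment case with LLOQ at 1/3.

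**The case against.** The strongest reply is that truncation may never occur. Sampling runs to six anticipated half-lives, with only 2^(−6) = 1.6% of exposure beyond it. In the one-compartment model the 91% case needs an LLOQ near 44% of the 2 mg peak, which is an assay that barely measures the lowest dose. This stands. A reader might infer that the end time does shorten with dose and that the 5% rate fails in this study. The documents do not support that, because they give no LLOQ, 2 mg exposure or CV.

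Second, Cmax and AUC(INF) are tested in the same sentence, and extrapolation and terminal-fit details are listed by subject. A pharmacokineticist who saw a slope above 1 on AUC(0-T) and about 1 on AUC(INF) would suspect truncation. This also stands. It rules out inferring that the whole proportionality assessment is unsound.

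Third, the SAP disclaims formal testing, and the study had ended before the SAP was written, so no later escalation in it depends on the result. That lowers the stakes. It does not remove the rule: 15.2.3.1 still attaches a verdict to p<0.05 for AUC(0-T), and that verdict would go into the report. AUC(0-T) was also pre-specified in protocol 9.4.3, but that does not change what the measure captures.

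**Conclusion.** The point holds conditionally. The mechanism follows from the SAP's own definitions: a subject-specific end time, later BLQ values dropped, and a p<0.05 label over a 30-fold dose range. Its size depends on when the 2 mg profiles become unquantifiable. False rejection is near nominal if that is at 192 h or later, slightly raised at 144 h (7%), and clearly raised at 120 h and earlier (12% to 91%). These figures assume a 40 h half-life, one-compartment kinetics, CV 30% and 3 active subjects in A5. A smaller CV or a distribution phase makes the inflation worse, and a larger CV makes it milder.

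The harm is limited to a spurious or conflicting AUC(0-T) verdict. The sponsor knows the LLOQ and can see at once which row of the table applies.

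**What to change.** In SAP 15.2.3.1:

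1. State that the AUC proportionality conclusion rests on AUC(INF), read alongside AUC%Extrap, which is already calculated. Keep Cmax as planned.
2. Add the power model on one common-window AUC, fixed before unblinding, as a supporting analysis. AUC(0-24) is the natural choice: protocol 8.5.3 defines it and protocol 9.4.3 uses it for Part B dose-linearity. A window chosen afterwards as the longest in which every subject is quantifiable would be data-driven.
3. Report the AUC(0-T) slope and interval descriptively, without the p<0.05 label.

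Do not add a hard 20% extrapolation exclusion. Where 2 mg is last quantifiable at 48 or 72 h, extrapolation is 44% or 29%, so the cap would remove the whole 2 mg cohort. That is 6 of 27 active subjects, and it cuts the dose range from 30-fold to 10-fold exactly where the bias is largest.

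The cost is a few lines of SAP text and one partial AUC from data already collected. The downside is that AUC(0-24) covers only 1 − 2^(−24/40) = 34% of total exposure at a 40 h half-life, so it is weak for detecting non-linear clearance. It supports AUC(INF) and does not replace it.

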### 15.2.4 Urine Pharmacokinetics

If applicable, descriptive statistics (n, mean, SD, geometric mean, %CV, median, min, and max) will be used to summarize the urine concentrations, amounts excreted and derived PK parameters for BMS-986251 in SAD part and treatment at each scheduled time interval and cumulative.

All available derived urine PK parameters will be included in the PK data set and reported, but only subjects with adequate PK profiles will be included in the summary statistics and statistical analysis.

All available individual subject urine BMS-986251 concentrations, amount excreted data, urine parameters will be listed.

## 16.1 Pharmacodynamic Analysis

The following PD assessment is planned in this study:

- ex-vivo inhibition (I) of IL-17 secretion in stimulated and unstimulated whole blood

### 16.1 Pharmacodynamic Variables

#### 16.1.1 IL-17 Inhibition in Whole Blood Variables

- The IL-17 concentrations in stimulated whole blood
- The IL-17 concentrations in unstimulated whole blood
- Percentage of IL-17 inhibition in stimulated whole blood

#### 16.1.2 IL-17 Inhibition PD Parameters

**Table 6** IL-17 PD Parameters (in whole blood)

Parameter	Description	SAS Programming Notes
Imax	Maximum observed inhibition	In SAS
tImax	Time of maximum observed inhibition	In SAS
tI>50%*	Time of inhibition above 50%	
tI>90%*	Time of inhibition above 90%	

\*if feasible

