#### 8.1.4 Pooling

Summary statistics will be calculated by study part, treatment (and time point, if applicable). Placebo data will be pooled across cohorts in Part A for descriptive statistics.

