### 9.4 Pharmacodynamic

All subjects who receive at least 1 dose of BMS-986251 or placebo and have any available data for the PD assessments.

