## 16.2 Pharmacodynamic Summaries

### 16.2.1 IL-17 Inhibition in Whole Blood

Individual data of IL-17 concentration in stimulated and unstimulated whole blood will be listed. Descriptive statistics (n, mean, SD, geometric mean, %CV, median, min, and max) of the IL-17 whole blood concentration will be summarize by treatment and time point. Levels of BLQ will be set to 0.

Percentage of IL-17 inhibition is calculated as:

$$\frac{[(\text{stimulated concentration at baseline} - \text{unstimulated concentration at baseline}) - (\text{stimulated concentration at Rx time point} - \text{unstimulated concentration at Rx time point})]}{(\text{stimulated concentration at baseline} - \text{unstimulated concentration at baseline})} * 100\%$$

Baseline is defined as the average concentration of pre-dose (T=-18.00 hr and T=0.00 hr). Percentage of IL-17 inhibition will be listed and summarized by treatment and time point. Linear plots of the arithmetic mean of percentage of IL-17 inhibition + SD in the whole blood by scheduled sampling times will be provided for SAD part. Linear plots of the combined individual percentage of IL-17 inhibition in the whole blood by scheduled sampling times will be provided by dose of BMS-986251 and placebo.

Mean plots of percentage of IL-17 inhibition versus mean BMS-986251 plasma concentration will be provided by treatment.

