### 16.2.2 Pharmacodynamic Parameters

Descriptive statistics (n, mean, SD, geometric mean, %CV, median, min, and max) will be used to summarize the calculated PD parameters by treatment. For tmax, tl>50%, and tl>90%, only n, median, min and max will be presented.

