**Table 10 Pharmacodynamic Sampling Schedule; Part A**

Sample Collection Time		Time (relative to dosing) hour:min	Blood Samples	
Study Day	Time (event)		Ex-vivo IL-17 Inhibition i	n Whole Blood
-1	Admission	NA	X	
1	0 h (pre-dose)	00:00	X	
1	1 h	01:00	X	
1	2 h	02:00	X	
1	4 h	04:00	X	
1	12 h	12:00	X	
2	24 h	24:00	X	
3	48 h	48:00	X	
5	96 h	96:00	X	
7	144 h	144:00	X	
11	240 h	240:00	X	

h = hour; IL-17 = interleukin-17; min = minute; NA = not applicable.

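### IL-17 Imax is the maximum of up to nine noisy ratios, so it is biased upward in every arm, and the SAP computes no placebo-adjusted inhibition to set beside it

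*SAP*

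**What the plan says.** SAP 16.1.2 (Table 6) defines Imax as "Maximum observed inhibition". SAP 16.2.1 expresses each reading as the percentage fall in net IL-17 (stimulated minus unstimulated) from the subject's own baseline, which is the mean of the two pre-dose samples. Part A has nine post-dose samples (SAP Table 10).

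The readings are then described: "Percentage of IL-17 inhibition will be listed and summarized by treatment and time point". Individual curves "will be provided by dose of BMS-986251 and placebo". For Imax and the other parameters, SAP 16.2.2 says that descriptive statistics "will be used to summarize the calculated PD parameters by treatment".

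Placebo is part of this. The PD set (SAP 9.4) is "All subjects who receive at least 1 dose of BMS-986251 or placebo and have any available data for the PD assessments", so placebo subjects also receive an Imax, and SAP 8.1.4 states: "Placebo data will be pooled across cohorts in Part A for descriptive statistics". SAP section 16 contains no difference from placebo, no model and no interval. Protocol 9.4.4 had planned a dose-response analysis that included Imax and left the details to the SAP. SAP section 16 has none, and SAP 7.1 does not list its removal among the changes.

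**The concern.** A maximum over repeated noisy readings picks out the most favourable error. With no drug, each single reading averages about zero, but the largest of nine does not. The inflation shrinks as true inhibition approaches 100%, so low doses gain most and the steps between doses look smaller than they are. The same noise can carry an undosed subject past the 50% threshold used for the time-above-50% parameter.

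A second gap does not depend on the maximum. Each subject is compared only with their own baseline, so any change in ex-vivo IL-17 shared by all subjects (time of day, confinement) enters the active-group figures. Pooled placebo, sampled at the same times, is the control that could remove it, but nothing is calculated with it.

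At stake is how the dose response is read for the planned measure of a secondary objective.

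**Working it through.** **The plan's own figure.** The only design probability is in SAP 6.1: 6 active subjects, 24% incidence, about 80% chance of seeing at least one event. It reproduces: 1 − 0.76^6 = 0.807. It concerns adverse events. The documents give no IL-17 variability, target inhibition or PD precision.

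**Inputs from the documents.** Post-dose samples at 1, 2, 4, 12, 24, 48, 96, 144 and 240 h, so nine (SAP Table 10). Baseline is the mean of two samples (SAP 16.2.1). Planned placebo in A1 to A4: 4 × 2 = 8, pooled (SAP Table 1, 8.1.4). Half-life about 40 h (protocol 8.1.1), used only to shape the assumed effect profile.

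**Assumptions, not in the documents.** Independent log-normal within-subject error in net IL-17 with CV 10 to 40%, and the true peak inhibitions shown below.

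**Formula.** I(t) = 100 × (1 − Y(t)/B), and Imax is the largest I(t). For a constant true inhibition e and multiplicative error, mean Imax = e + (1 − e) × P, where P is mean placebo Imax. The bias is (1 − e) × P, largest when e is small. At CV 20% (P = 25.0) it is 0.75 × 25.0 = 18.8 points for e = 25% and 0.10 × 25.0 = 2.5 points for e = 90%. An effect that wears off has fewer samples near its peak, so its bias is smaller, as simulated below.

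**No drug effect (200,000 simulated subjects per row).**

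| CV | Mean single reading | Mean Imax | Share with Imax above 50% |
|---|---|---|---|
| 10% | −0.5 | 13.6% | 0% |
| 20% | −2.0 | 25.0% | 2% |
| 30% | −4.5 | 34.3% | 19% |
| 40% | −8.0 | 41.9% | 40% |

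Additive error gives larger means at the same CVs: 14.4, 28.3, 41.6 and 54.1%.

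**Mean active Imax, with excess over the truth in brackets.**

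| True peak | CV 20% | CV 30% | CV 40% |
|---|---|---|---|
| 25% | 39.1 (+14.1) | 46.0 (+21.0) | 52.0 (+27.0) |
| 50% | 57.8 (+7.8) | 61.9 (+11.9) | 65.6 (+15.6) |
| 75% | 78.4 (+3.4) | 80.3 (+5.3) | 82.1 (+7.1) |
| 90% | 91.3 (+1.3) | 92.0 (+2.0) | 92.7 (+2.7) |

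The true spread from 25% to 90% is 65 points. It appears as 91.3 − 39.1 = 52.2, 92.0 − 46.0 = 46.0 and 92.7 − 52.0 = 40.7 points. At CV 10% the excess is small: 53.4 − 50 = 3.4 points for a true 50%.

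**Difference in Imax, active minus placebo (not planned in the SAP).** For a true 50% at CV 20/30/40%: 57.8 − 25.0 = 32.8; 61.9 − 34.3 = 27.6; 65.6 − 41.9 = 23.7. All fall below 50, because placebo carries the larger bias.

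**Possible repairs, CV 20/30/40%.**
- Baseline-adjusted log contrast with placebo at a fixed 4 h (6 active, 8 placebo, true 60%): 58.6 to 59.6%, nearly unbiased.
- Peak of the placebo-adjusted group curve: about 14/20/25% with no drug, so still biased upward.
- Individual maximum after subtracting placebo means: 59.7/66.5/73.7% for a true 50%, so not repaired.

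**Common shift (illustration).** If IL-17 fell by an assumed 20% in everyone at 12 h, a true 55% inhibition would read 1 − 0.80 × 0.45 = 64% without baseline noise. Simulated unadjusted means were 61 to 63%; the placebo-adjusted contrast gave 53 to 54%.

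**The case against.** The strongest reply is that this is a descriptive secondary analysis, in a plan written after the study was terminated for non-clinical findings. Observed Imax was prespecified in the protocol, no hypothesis is tested, and no decision or error rate depends on it. That stands, and it limits the weight of the point.

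Placebo is also not ignored. It is in the PD set, pooled, tabulated by time point and plotted. Time-point means carry no maximum bias, and a shared 12 h shift would be visible in the placebo row. A reader might infer that such a shift must be taken for drug effect; the documents do not support that. What is missing is the computed contrast and its interval.

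A reader might also infer that the plan understates the drug effect on Imax. That holds only for an active-minus-placebo difference in Imax, which no section plans; the reported active Imax errs the other way. Even for the difference, the understatement disappears with a constant effect, additive error and no ceiling.

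Nor do the documents show that placebo subjects will have sizeable apparent inhibition. That depends on a CV they do not state, and at 10% the mean is about 14% with essentially nobody above 50%.

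Finally, a log model is fragile here. SAP 16.2.1 sets values below quantification to zero, so net IL-17 can be zero or negative under strong inhibition. This stands, and the fix needs a rule for it.

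**Conclusion.** The point holds in a limited form. Imax is biased upward in every arm, most at low effect, so the active Imax that the SAP reports overstates peak inhibition at low doses and compresses the dose response. No placebo-adjusted estimate or interval is planned at any time point.

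The direction follows from the SAP's own definitions. The size does not: it rests on the assumed independent log-normal error, the CV range and the effect profile. Nine readings also assumes complete sampling. Cohort A5 was stopped during dosing, so its subjects may have fewer.

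Severity is minor to worthwhile, because PD is secondary and nothing is tested. The correction uses data already collected.

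**What to change.** In SAP 16.2.1, for Part A, add placebo-adjusted inhibition for each dose group against pooled placebo at every scheduled time point, with a 90% CI. Take it from a baseline-adjusted model of log net IL-17, reported as 100 × (1 − ratio to placebo). Where net values are zero or negative, report the difference in mean percent inhibition instead, and state the rule in advance.

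Base any dose-response statement on these contrasts at prespecified fixed times or on a fixed-window average, not on the peak of the adjusted curve. Keep individual Imax as descriptive only, shown beside placebo Imax with a note that it is positive without drug.

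The cost is one extra table and the rule for non-positive values. Intervals for 60 mg will be wide: SAP 7.1 records 4 subjects dosed in A5, with the active/placebo split not stated.
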